### 1 Month, 2 Month and 3 Month Post-Treatment Visits (+/- 7 Day Window)

- Continuance Criteria: patients will be released from study participation for the following reasons:
  - non-compliance with study procedures
  - development of a medical condition or taking a medication which would affect the study outcome, as covered in the exclusion criteria
  - disease progression or unacceptable toxicity of study drug, as assessed by the investigator
  - pregnancy
  - withdrawal of patient consent
  - protocol violation
  - lost to follow-up
  
- Review of Medical Records, if applicable
  
- Medical/Dental History update
  
- Concomitant Medications update
  
- Urine Pregnancy Test (if female of child bearing potential)
  
- Adverse Events

#### **4.5 Discontinuation of Protocol-Specified Therapy**

No dose reductions will be allowed in this study. Treatment with vismodegib may only be interrupted for up to:

- Two consecutive weeks if a patient becomes temporarily unable to swallow capsules
  
- Two consecutive weeks in case of an intolerable toxicity finding

A total up to eight weeks of dose interruptions (e.g., 4 x 2-week interruptions, 8 x 1-week interruptions, etc.) is allowed during the Treatment Phase.

Protocol-specified therapy may be discontinued for any of the following reasons:

- Progressive disease (PD)
  
- Unacceptable toxicity
  
- Patient election to discontinue therapy (for any reason)
  
- Physician's judgment

## 4.6 Subject Discontinuation

Study subjects may be discontinued from the study for any of the following reasons:

- non-compliance with study procedures
- development of a medical condition or taking a medication which would affect the study outcome, as covered in the exclusion criteria
- disease progression or unacceptable toxicity of study drug, as assessed by the investigator
- pregnancy
- withdrawal of patient consent
- protocol violation
- lost to follow-up

Should a patient decide to withdraw from the study or is discontinued by the investigator, all efforts will be made to complete the discontinuation visit procedures and assessments (see Appendix A).

In the event that a subject becomes pregnant during the study, the subject will be withdrawn from the study immediately upon confirmation of pregnancy. These subjects will be required to return to the study site to undergo discontinuation visit assessments. In addition, any documented pregnancy will be tracked and followed through outcome.

## 4.7 Study Discontinuation

The Genentech Study Center and the Principal Investigator have the right to terminate this study at any time. Reasons for terminating the study may include the following:

- The incidence or severity of adverse events in this or other studies indicates a potential health hazard to subjects
- Subject enrollment is unsatisfactory
- Data recording are inaccurate or incomplete
- Study protocol not followed

Both the investigator and Genentech, Inc. reserve the right to terminate the study at any time. Should this be necessary, both parties will arrange discontinuation procedures. In terminating the study, both the investigator and Genentech, Inc. will assure that adequate consideration is given to the protection of the patients' interests. All patients will undergo an exit examination if the study is terminated prematurely.

Patient's medical information obtained as a result of this study is considered confidential and disclosure to third parties other than those noted below is prohibited. Patients will receive written copies of all laboratory data, and radiographs to bring to their health care provider. All reports and communications relating to patients in this study will identify each patient only by their initials and number. Medical information resulting from a patient's participation in this study may be given to the patient's personal physician or to

the appropriate medical personnel responsible for the patient's welfare. Data generated as a result of this study are to be available for inspection on request by FDA or other government regulatory agency auditors, Genentech's medical monitor (or designee), and the Institutional Review Board (IRB).

## **4.8 Statistical Methods**

### **a. Analysis of the Conduct of the Study**

Accrual rates and sampling bias will be determined by computing the recruitment rate from among those identified as eligible.

Retention and compliance will be evaluated as the proportion of completers at the four primary time points: after 6 and up to 12 months of treatment, and then 1 and 2 years after treatment. We will detail and tabulate reasons for loss to follow-up and relate retention to baseline age, KCOT severity and between NBCSS-associated and sporadic cohorts.

### **b. Efficacy Analysis**

#### **i. Primary Endpoint**

The effect of GDC-0449 will be evaluated (at a significance level of 5% and controlling the false discovery rate) using Wilcoxon signed rank tests to compare the mean KCOT volume at baseline to those acquired at 6, 12, 24,36 and 48 months. These comparisons will also be accomplished using paired t-tests.

ii. Subject population for this analysis. As a primary intention to treat (ITT) analysis, we will analyze data from all randomized subjects who complete Phase 1. For these analyses, Phase 1 values will be substituted for missing observations. Should more than 20% of the data be missing at any observation interval, analysis of that interval will be abandoned. Deviations from this plan, for example, emergent interest in the analysis of the all-treated or protocol-compliant subjects, will be transparently pursued and reported.

iii. Treatment of missing data. Two secondary effectiveness analyses will either carry the last observation forward into missing cells, or use maximum likelihood estimates of those values. We expect the best estimate of efficacy is likely to lie within the limits set by these conservative (ITT) and liberal (LOCF, ML) treatments of missing data.

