#### **iv. Secondary Endpoints**

Secondary analysis will quantify the proportion of patients achieving minimal clinically significant changes in their tumors and comparing that to a theoretical expectation of 5% improvement with a Fisher exact test, and the effect of the *PTCH1* mutation on tumor volume reduction will be assessed with an independent samples t-test. These analyses will use the same population as the primary endpoint.

All analyses will be done using IBM SPSS Version 21.

v. Sample size determination. Twenty subjects will be recruited. Analysis of the primary endpoint is capable of detecting changes in tumor volume in the Wilcoxon tests of approximately 1.0 and .68 SD, assuming a 2-tailed type 1 error of 5% and power of 80% and then assuming either n=10 (separate analysis of the NBCSS-associated and sporadic cohorts) or n=20 (combined analysis of both cohorts), respectively (G\*Power, v3.1).

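### The 0.68 and 1.0 SD detectable effects are single-test, unadjusted, complete-data figures. Per-visit power under the planned false-discovery-controlled analysis is lower, and the visit list includes a month-48 CT that is not scheduled.

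*Combined protocol and SAP*

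**What the plan says.** Section 4.8 b.i sets out the primary efficacy analysis. Wilcoxon signed-rank tests, "at a significance level of 5% and controlling the false discovery rate", will "compare the mean KCOT volume at baseline to those acquired at 6, 12, 24,36 and 48 months". The next sentence adds a second test: "These comparisons will also be accomplished using paired t-tests".

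Section 4.8 b.ii covers missing scans: "Phase 1 values will be substituted for missing observations". It also sets a limit: "Should more than 20% of the data be missing at any observation interval, analysis of that interval will be abandoned".

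The sample-size paragraph (4.8 b.v) says that analysis of the primary endpoint is "capable of detecting changes in tumor volume in the Wilcoxon tests of approximately 1.0 and .68 SD". It assumes a two-tailed 5% error and 80% power, with n=10 for "separate analysis of the NBCSS-associated and sporadic cohorts" or n=20 for both cohorts combined. It mentions neither multiplicity nor missing data.

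Section 4.8 a, on study conduct, refers to "the four primary time points: after 6 and up to 12 months of treatment, and then 1 and 2 years after treatment". Volumetric CT after baseline is scheduled at 6 months and 1 year on treatment (4.4.3) and at 1 and 2 years after treatment (4.4.4). Appendix A agrees and adds only a discontinuation visit. Section 3.1 gives a 3-year study.

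**The concern.** There are two linked problems.

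1. The power statement does not describe the specified analysis. The plan tests several visits under false-discovery control and replaces missing follow-up volumes with the baseline value. The power figures carry neither feature. The procedure and the family are also unnamed. The plan does not say whether the paired t-tests count, or whether the separate cohort analyses do.

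2. The visit list has five entries, but the schedule supplies scans for four. Month 48 lies beyond the end of follow-up.

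Each visit is compared with baseline, so a reader may take 0.68 and 1.0 SD as what a given visit's adjusted comparison detects with 80% power. In a trial of 20 patients with cohorts of 10, a non-significant visit would then be read against a sensitivity that the analysis does not have. An undefined family also leaves open, until the data are seen, a choice that can change which visits are declared significant.

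**Working it through.** **Inputs from the documents.** Two-sided 5%, 80% power, n=10 or 20, effects of 1.0 and 0.68 SD (4.8 b.v). False-discovery control at 5%, baseline substitution and the 20% missing limit (4.8 b.i–ii). Four scheduled follow-up CTs (4.4.3, 4.4.4, Appendix A).

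**Assumptions, because the documents give none.** Benjamini-Hochberg over the four visits, normally distributed changes, between-visit correlation 0.3 to 0.7, and exact signed-rank p-values with zero changes dropped.

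**1. Reproducing the plan's figures.** The usual planning method for the signed-rank test uses n' = 3n/π and a noncentral t with n'−1 degrees of freedom and noncentrality d√n'.
- n=20: n' = 19.10; noncentrality = 0.68 × √19.10 = 2.97; power 80.3%. Effect for 80% power: 0.678 SD.
- n=10: n' = 9.55; noncentrality = 1.0 × √9.55 = 3.09; power 78.0%. Effect for 80% power: 1.026 SD.

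The stated figures are therefore right for one unadjusted test on complete data.

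**2. Limits that need no correlation or effect pattern.** Benjamini-Hochberg over four tests compares the ordered p-values with 0.05 × k/4, that is 0.0125, 0.025, 0.0375 and 0.05. It always rejects p ≤ 0.0125 and never rejects p > 0.05. Per-visit power therefore lies between the single-test powers at those two levels.

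| Case | Power at 0.0125 | Power at 0.05 |
|---|---|---|
| n=20, 0.68 SD, complete | 0.592 | 0.803 |
| n=10, 1.0 SD, complete | 0.470 | 0.784 |
| n=20, 20% missing (16 non-zero changes) | 0.441 | 0.683 |
| n=10, 20% missing (8 non-zero changes) | 0.251 | 0.610 |

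**3. Simulated power, complete data** (40,000 runs; correlation 0.3 / 0.7).

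| Where the effect is | n=20, month 12 | n=20, any visit | n=10, month 12 | n=10, any visit |
|---|---|---|---|---|
| Month 12 only | 0.603 / 0.594 | 0.615 / 0.609 | 0.481 / 0.474 | 0.492 / 0.484 |
| Both on-treatment visits | 0.670 / 0.665 | 0.814 / 0.752 | 0.562 / 0.565 | 0.714 / 0.658 |
| Equal at all four | 0.763 / 0.750 | 0.942 / 0.854 | 0.722 / 0.714 | 0.904 / 0.810 |

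**4. Missing scans.** A substituted baseline gives zero change, which the signed-rank test drops. Month-12 power over the same patterns is:
- 10% missing: 0.526–0.695 (n=20) and 0.427–0.596 (n=10).
- 20% missing: 0.443–0.616 and 0.261–0.505. This is the plan's ceiling, not an expected rate.

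**5. Per-visit effect detectable with 80% power (SD).**

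| Non-zero changes | Unadjusted | Equal at all four | Both on-treatment visits | One visit only |
|---|---|---|---|---|
| 20 | 0.678 | 0.712–0.720 | 0.772–0.780 | 0.828–0.832 |
| 10 | 1.018 | 1.081–1.098 | 1.253–1.262 | 1.382 |
| 16 (20% of 20 missing) | 0.781 | 0.810–0.823 | 0.879–0.888 | 0.956–0.965 |
| 8 (20% of 10 missing) | 1.248 | 1.335–1.352 | 1.485–1.494 | 1.893–1.915 |

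**6. Month 48.** Treatment of 12 months plus 24 months of follow-up ends at month 36, so the scheduled scans fall at months 6, 12, 24 and 36. Month 48 would be wholly missing, and the 20% rule would abandon it. If it were still counted as a fifth test, month-12 power at n=20 would be 0.557–0.720, against 0.594–0.763 with four tests.

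**7. Why the family must be stated.** If the combined set and both cohorts formed one family, there would be 3 × 4 = 12 tests, with a strictest step of 0.05/12 = 0.0042. A single test at that level has power of 41% (n=20) and 32% (n=10) by the planning method in step 1.

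**The case against.** The sample-size paragraph states its own conditions, and its figures are correct under them. It never says that they apply per visit or after adjustment. If detecting an effect means rejecting at one or more visits, equal effects give 85–94% (n=20) and 81–90% (n=10), above the claim. The lowest figures need shrinkage at one visit only, which is an unlikely course. With equal effects the loss is only about 4 to 5 points at n=20 and 6 to 7 at n=10. The adjusted SDs rest on assumptions that the sponsor did not make. Month 48 is a list error that the plan's own 20% rule would remove.

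Most of this stands as qualification. The any-visit figures and the modest loss under equal effects must be reported alongside the per-visit ones. It does not remove the point. The paragraph attributes its power to analysis of the primary endpoint, and that analysis is a set of adjusted visit comparisons. Even the any-visit reading falls short at n=10 if only the on-treatment visits carry the effect (66–71%). That pattern matters because two of the four scans come 1 and 2 years after the drug stops.

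A further objection is that the small-sample figures partly reflect the discreteness of the exact test. At the 0.0125 step that test attains only 0.0098 (n=10) and 0.0078 (n=8), and the planning formula would give 1.33 and 1.59 SD instead of 1.39 and 1.92. But using the normal approximation for the signed-rank p-value gives 1.53 SD at n=10 and 1.92 at n=8. The planning formula is the optimistic one here, so the exact figures do not overstate the cost.

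**Conclusion.** The concern holds. The stated effects are valid per-test figures, but the analysis as specified does not deliver 80% power at a given visit for them. That power cannot exceed the unadjusted value under Benjamini-Hochberg, and it was lower in every pattern computed. With complete data it lies within 59–80% at n=20 and 47–78% at n=10 for any effect pattern or correlation.

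These sizes depend on Benjamini-Hochberg, a family of four and normal changes. The simulated values within the limits also depend on the assumed correlations. The direction and the textual gaps do not depend on the simulations. Month 48 is a minor error in itself, but it leaves the number of tests unclear.

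**What to change.** - In 4.8 b.i, replace the month list with the four scheduled CT visits, defined by visit: 6 and 12 months on treatment, and 1 and 2 years after the end of treatment.
- Name the false-discovery procedure. State that the family is the four signed-rank visit comparisons within each analysis population (combined, and each cohort if analysed separately), with the paired t-tests as supportive.
- In 4.8 b.v, label 0.68 and 1.0 SD as per-test, unadjusted, complete-data figures.
- Add the per-visit adjusted figures with their assumptions: about 0.71–0.83 SD (n=20) and 1.1–1.4 SD (n=10) with complete data, and about 0.81–0.97 and 1.3–1.9 SD at the 20% missing ceiling. State that each range runs from equal effects at all visits to an effect at one visit only. If the sponsor chooses a different procedure or family, these figures should be recomputed for it.

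The cost is SAP wording only. No patients or scans are added, and the stated detectable effects become less favourable.

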### Phase II BCNS Study (SHH4685s)

The anti-BCC efficacy of vismodegib was tested in a randomized, double-blinded, placebo-controlled, Investigator-sponsored trial in Gorlin syndrome (BCNS) patients with surgically eligible BCCs [13-15]. Forty-one patients were randomized 2:1 to receive oral vismodegib (n=26) or placebo (n=15). After a mean follow up of 8 months (range, 1 to 15 months), the per-patient rate of new surgically eligible BCCs (SEBs) was lower with vismodegib than with placebo (2 vs. 29 cases per group per year, p<0.001), as was the size (percent change from baseline in the sum of the longest diameter) of existing clinically significant BCCs (–65% vs. –11%, p=0.003). In some patients, all BCCs clinically regressed. No tumors progressed during treatment with vismodegib. Patients receiving vismodegib routinely had Grade 1 or 2 AEs of loss of taste, muscle cramps, hair loss, and weight loss. Overall, 54% of patients (14 of 26) receiving vismodegib discontinued drug treatment due to AEs. At 1 month, vismodegib use had reduced the Hh pathway's target-gene expression in BCC cells by 90% (p<0.001) and diminished tumor-cell proliferation, but apoptosis was not affected. No residual BCC was detectable in 83% of biopsy samples taken from sites of clinically regressed BCCs. At the second pre-specified interim analysis, a data safety and monitoring board concluded that the pre-determined threshold for a significant difference between the two groups had been reached (p<0.0113), and the treatment with placebo in this arm was terminated. AEs reported in ≥10% of patients are summarized in Table 9 See the Vismodegib Investigator's Brochure and the U.S. package insert for additional details on nonclinical and clinical studies on vismodegib.

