### **Panoramic Radiograph and Volumetric CT Scan**

Tumor volume will be measured at baseline, and tumor response (reduction in tumor volume and recurrence) will be measured during the treatment phase and post-treatment phase by Panoramic Radiograph and Volumetric CT scan. The use of Panoramic Radiograph and Volumetric CT scan to measure the tumor volume are obtained for clinical assessment purposes only. No additional scans will be performed for research purposes. Disease progression during the treatment phase will be classified by an increase of at least 20%, with an absolute change greater than 5 mm in tumor size after 3 months of treatment. KCOTs grow within the bone. CT scan and panoramic radiograph are superior, with regard to sensitivity and specificity, in terms of evaluating bone involvement.

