#### **4.4.3 Phase 2: Treatment (1 Year)**

##### 1 Month, 3 Month, 6 Month and 1 Year Visit (+/- 7 Day Window)

- Continuance Criteria: patients will be released from study participation for the following reasons:
  - non-compliance with study procedures
  - development of a medical condition or taking a medication which would affect the study outcome, as covered in the exclusion criteria
  - disease progression or unacceptable toxicity of study drug, as assessed by the investigator
  - pregnancy
  - withdrawal of patient consent
  - protocol violation
  - lost to follow-up
  
- Review of Medical Records, if applicable
  
- Medical/Dental History update
  
- Concomitant Medications update
  
- Urine Pregnancy Test (if female of child bearing potential)
  
- Oral Cavity Assessment (soft & hard tissues, extraoral, head & neck)
  
- Physical Exam
  
- Clinical Laboratories (at 3 month, 6 month and 1 year visit)
  
- Genetic Testing for Blood (at 1 year visit)
  
- Genetic Testing for the Tumor (at 1 year visit)
  
- Vital Signs (blood pressure, heart rate, temperature)
  
- Panoramic Radiograph
  
- Volumetric CT Scan (at 6 month and 1 year visit)

- Skin Examination for NBCCS-associated KCOT patients at 6 month and 1 year visit
- Photographs of Skin Lesions, if applicable
- Compliance with Study Drug
  - Compliance with study drug will be checked by counting the capsules that were returned to the site versus the capsules that were administered to patient at the end of the last visit. Any discrepancy will be documented in the patient's chart and in the drug accountability log. Study reminders regarding compliance will be reviewed with the patient in order to maximize the proper use of the study drug.
- Study Drug Dispense until next visit
- Adverse Events

Upon discharge from the clinic, specific instructions will be given to patients regarding the use of the medication, as well as adequate study drug supplies until their next visit. Patients will be instructed the following:

- Not to donate blood or blood products while receiving GDC-0449 and for at least 24 months after the last dose of the study drug.
- Not to get pregnant during the study and for 24 months after the last dose of the drug (see more details in Appendix B)
- To take 150 mg of GDC-0449 orally once daily with or without food and to swallow capsules whole. Capsules should not be opened or crushed.

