APPENDIX A: SCHEDULE OF STUDY ASSESSMENTS & PROCEDURES

STUDY ASSESSMENTS & PROCEDURES	SCREENING PHASE	TREATMENT PHASE (1 YEAR)											POST TREATMENT FOLLOW UP (2 YEARS)							
	BASELINE VISIT	1 MONTH POST DOSING	2 MONTH POST DOSING	3 MONTH POST DOSING	4 MONTH POST DOSING	5 MONTH POST DOSING	6 MONTH POST DOSING	7 MONTH POST DOSING	8 MONTH POST DOSING	9 MONTH POST DOSING	10 MONTH POST DOSING	11 MONTH POST DOSING	1 YEAR POST DOSING	1 MONTH POST TREATMENT	2 MONTH POST TREATMENT	3 MONTH POST TREATMENT	7 MONTH POST TREATMENT	1 YEAR POST TREATMENT	2 YEARS POST TREATMENT	DISCONTINUATION VISIT
		+/- 7 DAYS																		
Informed Consent & Screening	X																			
Review of Inclusion/Exclusion Criteria	X																			
Review of Medical Records, if applicable	X	X	X	X	X	X	X	X	X	X	X	X	X	X	X	X	X	X	X	X
Medical/Dental History	X	X	X	X	X	X	X	X	X	X	X	X	X	X	X	X	X	X	X	X
Concomitant Medications	X	X	X	X	X	X	X	X	X	X	X	X	X	X	X	X	X	X	X	X
Demographics (height, weight)	X																			
Urine Pregnancy Test, if female patient of child bearing potential		X	X	X	X	X	X	X	X	X	X	X	X	X	X	X	X	X	X	X
Serum pregnancy test, if female patient of child bearing potential	X	*	*	*	*	*	*	*	*	*	*	*	*	*	*	*	*	*	*	*
Oral Cavity Assessment (soft & hard tissues)	X	X		X			X									X	X	X	X	
Physical Exam	X	X		X			X						X							X
Clinical Laboratories	X			X			X						X							X
Genetic Testing of Blood	X												X							X
Genetic Testing of the Tumor, if biopsy on excision	X												X							X
Vital Signs (BP, HR, temperature)	X	X		X			X						X				X	X	X	X
Verification of KCOT Diagnosis	X																			
Biopsy of Tumor, if applicable	X																			
Panoramic Radiograph	X	X		X			X						X				X	X	X	X
Volumetric CT Scan	X						X						X					X	X	X
Skin Examination for NBCCS-associated KCOT patients	X						X						X					X		X
Photographs of Skin Lesions, if applicable	X						X						X					X		X
Study Drug Administration – First Dose	X																			
Study Drug Dispense until next visit / Compliance with study drug	X	X	X	X	X	X	X	X	X	X	X	X	X							
Continuance Criteria/Study Reminders		X	X	X	X	X	X	X	X	X	X	X	X	X	X	X	X	X	X	
Adverse Events	X	X	X	X	X	X	X	X	X	X	X	X	X	X	X	X	X	X	X	X
Study completion, Discharge																				X

\* Any positive urine pregnancy test must be confirmed by a serum pregnancy test.

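### Setting missing tumour volumes to baseline is not assured to be conservative, and Section 4.8 b gives the scheduled discontinuation-visit CT no place in the primary analysis

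*Combined protocol and SAP*

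**What the plan says.** Section 4.8 b.i compares baseline volume with later volumes by Wilcoxon signed-rank tests and paired t-tests, "at a significance level of 5% and controlling the false discovery rate". For missing volumes in the primary intention-to-treat analysis, b.ii says: "For these analyses, Phase 1 values will be substituted for missing observations". An interval with more than 20% missing is not analysed. Section b.iii adds last observation carried forward (LOCF) and maximum likelihood (ML) as secondary analyses, and expects the best estimate to lie within "the limits set by these conservative (ITT) and liberal (LOCF, ML) treatments of missing data".

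The reasons for release in 4.4.3, 4.4.4 and 4.6 include "disease progression or unacceptable toxicity of study drug, as assessed by the investigator". Section 4.4 defines progression during treatment as "an increase of at least 20%, with an absolute change greater than 5 mm in tumor size after 3 months of treatment", without saying whether the increase is counted from baseline or from the smallest size reached. For patients who leave, 4.6 says "all efforts will be made to complete the discontinuation visit procedures and assessments". The row "Volumetric CT Scan" in Appendix A is marked at baseline, 6 months, 1 year, 1 and 2 years post-treatment, and the discontinuation visit. Section 4.8 b does not mention that last scan.

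**The concern.** Replacing a missing volume by the baseline volume gives that patient a change of exactly zero. Whether this works against the drug depends on where the tumour would have been. Below baseline, zero understates the benefit. Above baseline, zero hides growth. Since progression is a reason for release, some of the missing volumes may belong to patients whose tumours grew.

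The plan already schedules the scan that would show which case applies. Read literally, though, the leaver's next scheduled volume is missing and is reset to baseline even when a volume was measured at discontinuation. At stake is the primary efficacy result of a single-arm trial of 20 patients: lost power and a diluted mean in the likelier case and, less likely, a result described as conservative that favours the drug.

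**Working it through.** **1. The plan's own figure.** Section 4.8 b.v gives detectable changes of about 0.68 SD (n=20) and 1.0 SD (n=10) at two-tailed 5% and 80% power. A noncentral t calculation with n multiplied by 3/π (the efficiency of the signed-rank test for normal data) gives 0.678 and 1.026 SD, with power of 80.3% at 0.68 and 78.0% at 1.0. The figures reproduce.

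**2. Direction of the substitution.** The substituted mean equals (share observed) × (mean of the observed). The error against the leavers' actual volumes is (share missing) × (leavers' mean change). Take n=20, 4 missing (the most the 20% limit allows) and an observed mean of -0.68 SD. The substituted mean is 0.80 × (-0.68) = -0.544 in every case below.

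| Leavers' actual change (assumed) | Actual mean | Substitution is |
|---|---|---|
| -0.68 SD | -0.680 | conservative |
| 0 | -0.544 | neutral |
| +0.68 SD | -0.544 + 0.20 × 0.68 = -0.408 | too favourable |

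**3. The bracket in b.iii can fail.** Assume nine patients at -0.50 SD and one released at +1.0 SD who would later reach +1.5 SD.
- Actual mean: (9 × -0.50 + 1.5)/10 = -0.30
- LOCF from the discontinuation CT: (9 × -0.50 + 1.0)/10 = -0.35
- Baseline substitution: (9 × -0.50 + 0)/10 = -0.45

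The analysis labelled conservative is the most favourable of the three, and the actual mean lies outside both limits.

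**4. Power when leavers are a random subset (toxicity-type loss).** Simulated trials, normal changes with SD 1, planned effects, exact signed-rank test, zero differences dropped, one unadjusted time point:

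| Missing (n=20 / n=10) | Power |
|---|---|
| none | 80% / 78% |
| 2 / 1 | 75% / 68% |
| 4 / 2 | 68% / 61% |

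A dropped zero leaves the test exactly as if the patient had been left out. The paired t-test behaves almost the same: 72% with or without the substituted patients at n=20, and 67% against 68% at n=10. So the fall is the cost of having no volume for these patients. What substitution adds is dilution of the mean: 0.80 × 0.68 = 0.54 and 0.80 × 1.0 = 0.80.

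**5. False shrinkage when there is no true mean change** (nominal 2.5%, 4 / 2 missing, one unadjusted time point, a progressor being the largest grower at that visit):

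| Progressors among the missing | n=20 / n=10 |
|---|---|
| none | 2.2% / 2.0% |
| one | 5.4% / 6.4% |
| 17.5% of leavers | 5.0% / 3.7% |
| all (upper bound) | 32% / 17% |

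The 17.5% is borrowed from the large basal cell carcinoma safety study in 1.3.1.1: 70 of 400 drug stops were for progression.

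If the growth is seen on one scan and only later visits are missing (between-visit correlation 0.3 to 0.8), the 17.5% mix gives 2.7-4.2% / 2.2-3.1% unadjusted. With Benjamini-Hochberg control over the four post-baseline CT times (6, 12, 24 and 36 months; Appendix A has no 48-month scan), it gives 0.8-2.2% / 0.5-1.4% per time point. For any of the four it is 2.8-3.9% / 1.8-2.6%, against 1.8-2.4% / 1.6-1.9% with no loss.

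**The case against.** The strongest reply is that the label describes the likely leaver correctly. In the Gorlin-syndrome study in 1.3.1.1, "No tumors progressed during treatment with vismodegib", while 14 of 26 patients on drug (54%) stopped for adverse events. Section 4.4 also judges unanticipated growth on drug to be highly unlikely. This stands for the treatment phase. It does not cover follow-up off drug, where the same release rule applies and the documents give no regrowth rate for these tumours.

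Progression found on a scheduled CT is observed at that visit, so only later visits are reset. That also stands, and it is why the later-visit figures are smaller.

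The 20% limit caps the problem. If leaving matched the adverse-event stop rates of 35.6% and 54% in the cited studies (about 7 and 11 of 20), the chance that at most 4 of 20 leave would be 11% and 0.2%, and the interval would usually be abandoned. Those are drug stops in other studies, not missing scans here, so they show only that the figures apply to intervals within the limit.

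LOCF is prespecified and would naturally pick up the discontinuation CT, and b.iii is worded as an expectation. But LOCF is secondary, its use of that scan is not stated, and the primary rule remains as written.

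A reader might infer that substitution itself causes the loss of power. It does not, as step 4 shows. A reader might also infer that LOCF should become the primary rule throughout. The documents do not support that: the operable basal cell carcinoma study in 1.3.1.1 reports a lack of durable response. If on-drug shrinkage were carried to 24 and 36 months while tumours had returned to baseline, false shrinkage there would be about 6.9% / 6.1%, against 2.2% / 1.9% under the present rule.

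**Conclusion.** The point holds in a limited form. Baseline substitution is conservative for leavers below baseline and too favourable for leavers above it, so neither the label nor the statement that the best estimate lies between the two limits is assured. Separately, a scheduled CT volume has no stated place in the primary analysis.

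The likelier harm is unused information: power of 68% / 61% instead of 80% / 78% at the 20% limit, and means diluted to -0.54 and -0.80 SD. The less likely harm is a false finding of shrinkage, about 5% / 6.5% with one progressor among the missing at a single unadjusted time point. After false discovery rate control in the likelier mix it stays below 2.5% per time point. A reader might infer that the primary analysis is generally biased toward the drug; the documents do not support that.

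The directions follow from the text and simple arithmetic. The sizes rest on assumptions the documents do not supply: normal changes, the share of progressors among leavers, the between-visit correlation, and growth or regrowth after leaving. Severity is minor to should-fix; confidence is moderate.

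**What to change.** In 4.8 b.ii:
1. For patients who leave during the treatment phase, take the discontinuation CT volume as the observed value for the next on-treatment CT time point (6 or 12 months), whatever the reason for leaving. Do not count it as observed at 24 or 36 months unless it falls within a prespecified window of that visit; otherwise a scan taken soon after the drug stops could stand in for a much later result.
2. Keep baseline substitution for the remaining missing volumes, except that a patient whose last CT is above baseline takes that last volume. State how zero differences are handled, and report the number of filled values per time point.
3. Continue to count carried and substituted values as missing for the 20% limit.

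In 4.8 b.iii:

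4. State that LOCF uses the discontinuation CT.
5. Delete the conservative and liberal labels and the sentence that places the best estimate between them.

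Do not make LOCF the primary rule at 24 and 36 months.

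The cost is SAP wording and slight programming; the scan is already scheduled. The estimate can become slightly less favourable. At the on-treatment time point that is filled, power at the planned effects with 4 / 2 leavers would be 80% / 78% if every discontinuation CT is obtained and shows the full effect, 75% / 68% if half are obtained, and 71% / 68% if they show half the effect, against 68% / 61% now.
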